5.2 Secondary Efficacy Endpoints

The secondary efficacy endpoints are:

- change in satisfaction for each TSQM domain from Visit 2 (Day 30) to Visit 4 (Day 90) for naïve BID patients
- change in satisfaction for each TSQM domain from Visit 2 (Day 30) to Visit 5 (Day 120) for naïve TID patients
- change in total qADAM score from Visit 1 (Day 0) to Visit 4 (Day 90) for non-naïve BID patients
- change in total qADAM score from Visit 1 (Day 0) to Visit 5 (Day 120) for non-naïve TID patients
- change in total qADAM score from Visit 1 (Day 0) to Visit 4 (Day 90) for naïve BID patients
- change in total qADAM score from Visit 1 (Day 0) to Visit 5 (Day 120) for naïve TID patients
- change in total qADAM score from Visit 1 (Day 0) to Visit 5 (Day 120) for non-naïve ALL patients
- change in total qADAM score from Visit 1 (Day 0) to Visit 5 (Day 120) for naïve ALL patients
- change in total qADAM score from Visit 1 (Day 0) to Visit 5 (Day 120) for non-naïve and naïve ALL patients

- patient preference of therapy as measured by Part A of the Treatment Preference and Use Questionnaire at Visit 1 (Day 0) for the following groups of patients:
 - non-naïve and naïve ALL
 - non-naïve ALL
 - naïve ALL
 - non-naïve BID
 - naïve BID
 - non-naïve TID
 - naïve TID
- patient preference of therapy as measured by Part B of the Treatment Preference and Use Questionnaire for the following groups of non-naïve patients:
 - BID at Visit 4 (Day 90)
 - TID at Visit 4 (Day 90)
 - TID at Visit 5 (Day 120)
- patient preference of therapy as measured by Part C of the Treatment Preference and Use Questionnaire for the following groups of naïve patients:
 - BID at Visit 4 (Day 90)
 - TID at Visit 4 (Day 90)
 - TID at Visit 5 (Day 120)
- Natesto™ dosing frequency by hypogonadism treatment status (naïve/non-naïve) assigned at Visit 4 (Day 90)

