5.4 Exploratory Endpoints

Exploratory endpoints will include:

- change in satisfaction for each TSQM domain from Visit 1 (Day 0) to Visit 5 (Day 120) for non-naïve ALL patients
- change in satisfaction for each TSQM domain from Visit 2 (Day 30) to Visit 5 (Day 120) for naïve ALL patients

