6.2 BID Intent-to-Treat (ITT) Population

The BID ITT population includes all patients who received at least one dose of study drug, are part of the BID treatment group and have a valid post-dose efficacy measurement at Visit 2 (Day 30) or Visit 3 (Day 60) or Visit 4 (Day 90). Data will be analysed using the BID ITT population as per the Table Mock-Up (TMU) document.

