7.3 Missing Data

Dates with missing day will be imputed as the 15th. Dates with both missing day and month will be imputed as July 1st. Date of hypogonadism diagnosis will be imputed.

Missing TSQM domain scores for both the BID and TID treatment groups will be imputed using LOCF (Last Observation Carried Forward). For LOCF to apply there must be at least a Visit 2 domain score available so that the patient had sufficient exposure to give a measurable change. The TSQM domain scores will be calculated based on the LOCF domain. Summaries for paired change from Visit 1/Day 0 will require both TSQM domain scores at Visit 1/Day 0 and Visit 2/Day 30 to be available to be included in output. Summaries for paired change from Visit 2/Day 30 will require the TSQM domain scores at Visit 2/Day 30 to be available to be included in output.

Missing qADAM questions for both the BID and TID treatment groups will be imputed using LOCF (Last Observation Carried Forward). For LOCF to apply there must be at least a Visit 2 question available so that the patient had sufficient exposure to give a measurable change. The total qADAM score will be calculated based on the LOCF items. Summaries for paired change

from Visit 1/Day 0 will require both total qADAM scores at Visit 1/Day 0 and Visit 2/Day 30 to be available to be included in output.

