9.2 Secondary Efficacy Analyses

The following secondary efficacy analyses will be performed using the ITT and the respective PP populations where indicated.

BID Treatment Group:

TSQM domain scores at Visit 2, Visit 3 and Visit 4 will be summarized and presented descriptively for naïve patients. There are three domains which include effectiveness (3 items), convenience (3 items) and global satisfaction (3 items). (ITT/PP)

TSQM domain change from baseline (Visit 2) scores at Visit 3 and Visit 4 (secondary endpoint) will be summarized and presented descriptively for naïve patients using 2 different approaches, LOCF and no LOCF. Change from baseline scores will be analysed using a two-sided paired t-test or a non-parametric equivalent if warranted by the data. (ITT/PP)

Total qADAM scores at Visit 1, Visit 2, Visit 3 and Visit 4 will be summarized and presented descriptively for non-naïve patients. (ITT/PP)

Total qADAM change from baseline (Visit 1) scores at Visit 2, Visit 3 and Visit 4 will be summarized and presented descriptively for non-naïve patients using 2 different approaches, LOCF and no LOCF. Change from baseline scores will be analysed using a two-sided paired t-test or a non-parametric equivalent if warranted by the data. (ITT/PP)

Total qADAM scores at Visit 1, Visit 2, Visit 3 and Visit 4 will be summarized and presented descriptively for naïve patients. (ITT/PP)

Total qADAM change from baseline (Visit 1) scores at Visit 2, Visit 3 and Visit 4 will be summarized and presented descriptively for naïve patients using 2 different approaches, LOCF and no LOCF. Change from baseline scores will be analysed using a two-sided paired t-test or a non-parametric equivalent if warranted by the data. (ITT/PP)

Part A questions 5, 6, 7, 8, 9, 10 and 11 of the Patient Preference and Use Questionnaire at Visit 1 will be summarized and presented descriptively/categorically for non-naïve and naïve patients. (ITT)

TID Treatment Group:

TSQM domain scores at Visit 2, Visit 3, Visit 4 and Visit 5 will be summarized and presented descriptively for naïve patients. There are three domains which include effectiveness (3 items), convenience (3 items) and global satisfaction (3 items). (ITT/PP)

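### In the LOCF tables, Section 7.3 gives naïve patients with only a Visit 2 TSQM score a change of exactly zero, and lets a score from before the Day 90 dose increase stand as a TID patient's Day 120 value

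*SAP*

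**What the plan says.** SAP Section 7.3 imputes missing TSQM domain scores by LOCF in both dose groups, on the condition that "there must be at least a Visit 2 domain score available so that the patient had sufficient exposure to give a measurable change". It then sets two entry rules for the paired summaries:

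- Change from Visit 1: "Summaries for paired change from Visit 1/Day 0 will require both TSQM domain scores at Visit 1/Day 0 and Visit 2/Day 30", that is, the baseline and one post-baseline score.
- Change from Visit 2: "Summaries for paired change from Visit 2/Day 30 will require the TSQM domain scores at Visit 2/Day 30 to be available", that is, one score only.

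Visit 2 is the naïve patients' TSQM baseline. Section 5.2 lists "change in satisfaction for each TSQM domain from Visit 2 (Day 30) to Visit 4 (Day 90) for naïve BID patients", Section 9.2 analyses "TSQM domain change from baseline (Visit 2) scores at Visit 3 and Visit 4 (secondary endpoint", and Section 5.4 adds "change in satisfaction for each TSQM domain from Visit 2 (Day 30) to Visit 5 (Day 120) for naïve ALL patients". For the BID ITT population, Section 6.2 takes in patients who "are part of the BID treatment group and have a valid post-dose efficacy measurement at Visit 2 (Day 30) or Visit 3 (Day 60"; its list of alternatives ends with the Day 90 visit, so a Visit 2 score alone qualifies.

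Section 3.0 places the dose increase at Day 90 (Visit 4). The TID endpoints in Sections 5.1 and 5.2 are at Visit 5 (Day 120), but TID ITT membership (Section 6.3) does not require a Visit 5 score. For qADAM, missing items are carried forward and "The total qADAM score will be calculated based on the LOCF items". Section 7.3 does not mention the dose change. It is also silent on Early Termination scores, although the schedule in Section 3.0 collects both questionnaires at that visit and Section 7.2 lists it as an analysis time point.

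Sections 9.1 to 9.3 present each change analysis with and without LOCF and do not say which leads.

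**The concern.** The two entry rules do not match. For non-naïve patients the Visit 2 requirement guarantees one measured change. For naïve patients the same visit is the baseline, so requiring it guarantees exposure to the drug but no measured change. LOCF then supplies the second half of the pair by copying the first.

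The second gap concerns what the Day 120 row represents. Visit 5 is the only routine questionnaire visit after the increase. Any scheduled score carried into it was therefore taken before the increase, possibly at the very visit where symptoms led to it.

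At stake are the descriptive results that this uncontrolled study mainly reports. In the LOCF tables, the mean, SD and median for naïve patients would include changes that nobody measured, and those patients would drop out of the missing count. The TID Day 120 row could contain BID-phase data under a TID label.

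**Working it through.** The SAP gives no effect size, SD or dropout rate, so it has no figure to reproduce. Every numerical input below is an assumption.

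**Step 1. Apply the rules to example patients.**
- Naïve, Visit 2 = 60, nothing later: LOCF gives Visit 3 = 60 and Visit 4 = 60. Change at both visits = 60 − 60 = 0.
- Naïve, Visits 2 and 4 observed, Visit 3 missing: the Visit 4 change is real, but the Visit 3 change is again exactly 0.
- TID, Visits 1 to 4 = 50, 60, 62, 55, Visit 5 missing: LOCF gives Visit 5 = 55, the Day 90 score. The Day 120 change from Visit 1 is 55 − 50 = 5, with no TID-phase observation behind it.

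**Step 2. Which analyses are reached.**
- Automatic zeros: naïve BID TSQM (secondary) and the naïve ALL Visit 3 and Visit 4 summaries. A patient who stops before Visit 4 cannot have moved to TID, so naïve TID is touched only through missed questionnaires. The primary TSQM endpoints and all qADAM endpoints use Visit 1 as baseline and are not affected.
- Carry across the increase: the LOCF versions of TSQM change to Day 120 in non-naïve TID (primary) and naïve TID (secondary), and of the TID Day 120 qADAM endpoints.

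**Step 3. Size of the automatic zeros.** Assume 40 naïve BID patients. Those with a later score have normally distributed change with mean μ = 10 and SD σ = 20. A share f (4, 8 or 12 patients) has Visit 2 only.
- LOCF mean = (1 − f)μ
- LOCF variance = (1 − f)(σ² + μ²) − mean² = 369, 336, 301
- LOCF SE = √(variance/40); observed-case SE = 20/√(40(1 − f))
- LOCF median m solves f + (1 − f)Φ((m − 10)/20) = 0.5. At f = 30% the point mass at zero holds it: 0.7 × Φ(−0.5) = 0.216 lies below zero, and 0.216 + 0.3 = 0.516.

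| LOCF v observed | f = 10% | f = 20% | f = 30% |
|---|---|---|---|
| Mean | 9 v 10 | 8 v 10 | 7 v 10 |
| SD | 19.2 v 20 | 18.3 v 20 | 17.3 v 20 |
| Median | 7.2 v 10 | 3.6 v 10 | 0 v 10 |
| SE | 3.04 v 3.33 | 2.90 v 3.54 | 2.74 v 3.78 |
| t | 2.96 v 3.00 | 2.76 v 2.83 | 2.55 v 2.65 |
| Two-sided p (df 39 v 35, 31, 27) | 0.0052 v 0.0049 | 0.0088 v 0.0081 | 0.0147 v 0.0134 |

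The LOCF SD is below σ whenever μ < σ/√(1 − f), which is 1.12 SD at f = 20%. In these cases the SE shrinks as more data go missing.

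**Step 4. Which run is nearer the truth.** At f = 20%, let the unobserved patients' true mean change be d. The true overall mean is 8 + 0.2d, which is 6, 8 or 10 for d = −10, 0 or +10. LOCF (8) is off by +2, 0 or −2; observed cases (10) by +4, +2 or 0. Neither run is better in all three cases.

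**Step 5. Carry into TID Visit 5.** Let the mean change be 10 in patients with an observed Visit 5, and m4 the carried Visit 4 change in the rest. The LOCF mean is 10(1 − f) + f·m4. At f = 20%, m4 = 5, 10 or 15 gives 9, 10 or 11. The sign depends wholly on m4, which the SAP does not determine.

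**The case against.** **Parallel analyses.** Every affected analysis has a no-LOCF version that shows the missing counts. Sections 9.1 and 9.2 also use the per-protocol sets, which require completion of Visit 4 (BID) or Visit 5 (TID). Section 8.0 calls the p-values exploratory. All of this stands. It limits the harm to the LOCF tables and leaves the per-protocol run exposed only where a completer missed a questionnaire.

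**No clear direction of harm.** Step 4 shows that LOCF can be nearer the truth than observed cases. This stands too, so there is no argument here for preferring one run. The objection is that an unmeasured change is presented as a measured one.

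**The exposure rationale.** A naïve patient at Day 30 has had the exposure that Section 7.3 speaks of. That is right. What fails is the link from exposure to a measurable change when Visit 2 is itself the baseline.

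**TID membership.** Section 7.1 ties the TID group to having titrated up, with Visit 5/Day 120 in brackets. If membership is read from attendance at Visit 5, the second problem shrinks to missing questionnaires at an attended visit. Section 6.3, and the dosing-frequency endpoint assigned at Visit 4 in Section 5.2, point the other way. The text does not settle it.

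**Early Termination.** A score taken after the increase could be the one carried. Section 7.3 neither says so nor rules it out, so a pre-increase score can fill Visit 5 but need not.

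**Conclusion.** Both problems follow from the wording of Section 7.3, and both are confined to the LOCF run, chiefly on the ITT population. Under the assumptions shown, 10% to 30% of naïve BID patients with Visit 2 only would lower the LOCF mean from 10 to between 9 and 7, lower the median more, and narrow the SE. The test result hardly changes. The correction should be made, but it does not call the study's conclusions into question.

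A reader might infer more, and the document does not support it:

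- That LOCF manufactures significance. The p-values barely move and are in fact slightly larger under LOCF.
- That naïve ALL at Day 120 is filled with zeros. Visit-2-only patients are BID patients, who have no Visit 5, so this happens only if LOCF is extended to Visit 5 for them. Section 7.3 does not say that it is.
- That the TID Day 120 result is understated. Step 5 shows that the sign is unknown.
- That every TID patient without a Visit 5 is affected. Section 7.1 may exclude those who did not attend.

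**What to change.** Amend Section 7.3 as follows.

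1. Include a patient in the LOCF summary of TSQM change from Visit 2 at a given visit only if at least one TSQM score after Visit 2, and at or before that visit, was observed. An Early Termination score within that time counts. Tying the rule to each visit also removes the zero at Visit 3 for a patient with Visits 2 and 4 only.
2. In TID-group Visit 5 summaries, do not carry TSQM domain scores, or a wholly missing qADAM, from Visit 4 or earlier into Visit 5.
3. State that Early Termination scores feed LOCF under both rules, for TID Visit 5 only if obtained after the increase. Single missing qADAM items at an attended Visit 5 may still be filled, but report how many Day 120 totals contain items carried from before the increase.

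This does not settle how BID patients enter the ALL-group Day 120 summaries.

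The cost is a few sentences, a filter in the SAS code and one count. The LOCF summaries will hold fewer patients, and TID Visit 5 with LOCF will lie close to the no-LOCF result and add little as a second analysis.

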7.4 Early Terminations

Patients who withdraw from the study before Visit 6 (Day 150) are considered “early terminations.”

8.0 ANALYSIS STRATEGY

A Table Mock-Up (TMU) document which will illustrate the details of presentation and analysis for data collected in this study will accompany this document. A brief discussion of the presentation, planned inferences, and statistical methods follows below. Data not presented in the TMU document will be provided in listings.

Continuous variables will be summarized descriptively by number of observations, number of missing observations, mean, standard deviation, median, 1st quartile, 3rd quartile, minimum and maximum. Categorical variables will be summarized descriptively as frequency counts and percentages.

A number of p-values may be presented in the reported tables for exploratory purposes. Statistical testing will be performed at the two-sided 0.05 significance level unless otherwise specified in the sections that follow. These p-values will not be adjusted for multiple comparisons.

9.0 EFFICACY ANALYSES

9.1 Primary Efficacy Analyses

The primary efficacy analyses will be performed using the ITT and the respective PP populations.

BID Treatment Group:

TSQM domain scores at Visit 1, Visit 2, Visit 3 and Visit 4 will be summarized and presented descriptively for non-naïve patients. There are three domains which include effectiveness (3 items), convenience (3 items) and global satisfaction (3 items).

TSQM domain change from baseline (Visit 1) scores at Visit 2, Visit 3 and Visit 4 (primary endpoint) will be summarized and presented descriptively for non-naïve patients using 2 different approaches, LOCF and no LOCF. Change from baseline scores will be analysed using a two-sided paired t-test or a non-parametric equivalent if warranted by the data.

TID Treatment Group:

TSQM domain scores at Visit 1, Visit 2, Visit 3, Visit 4 and Visit 5 will be summarized and presented descriptively for non-naïve patients. There are three domains which include effectiveness (3 items), convenience (3 items) and global satisfaction (3 items).

TSQM domain change from baseline (Visit 1) scores at Visit 2, Visit 3, Visit 4 and Visit 5 (primary endpoint) will be summarized and presented descriptively for non-naïve patients using 2 different approaches, LOCF and no LOCF. Change from baseline scores will be analysed using a two-sided paired t-test or a non-parametric equivalent if warranted by the data.

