2.3 Exploratory Objectives

Exploratory objectives will include analysis of the rate of change of the primary or secondary efficacy measures over the treatment period be that 90 days for patients on Natesto™ BID or 120 days for patients on Natesto™ TID.

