5.0 ANALYSIS ENDPOINTS

5.1 Primary Efficacy Endpoints

Primary efficacy is the self-reported patient satisfaction with treatment assessed by the Treatment Satisfaction Questionnaire for Medication (TSQM), a validated, 9-item instrument with domains for Effectiveness, Convenience and Global Satisfaction.

The primary efficacy endpoints are:

- change in satisfaction for each TSQM domain from Visit 1 (Day 0) to Visit 4 (Day 90) for non-naïve BID patients
- change in satisfaction for each TSQM domain from Visit 1 (Day 0) to Visit 5 (Day 120) for non-naïve TID patients

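### The primary TSQM change is analysed with LOCF and with observed cases, with no lead and no stated missing-data assumption; a likelihood-based repeated-measures model is a better lead when dropout follows recorded scores

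*SAP*

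**What the plan says.** Section 5.1 sets two primary endpoints: "change in satisfaction for each TSQM domain from Visit 1 (Day 0) to Visit 4 (Day 90) for non-naïve BID patients" and "change in satisfaction for each TSQM domain from Visit 1 (Day 0) to Visit 5 (Day 120) for non-naïve TID patients".

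Section 9.1 summarises the change at each visit "using 2 different approaches, LOCF and no LOCF". The test is applied visit by visit: "Change from baseline scores will be analysed using a two-sided paired t-test or a non-parametric equivalent if warranted by the data". On populations: "The primary efficacy analyses will be performed using the ITT and the respective PP populations".

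Section 8.0 sets the level ("Statistical testing will be performed at the two-sided 0.05 significance level unless otherwise specified"), leaves it unadjusted, and describes the status of the results: "A number of p-values may be presented in the reported tables for exploratory purposes".

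Other sections that bear on the point:

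- **Section 7.3** applies LOCF only when a Visit 2 score exists, and admits a patient to the paired change from Visit 1 only when Visits 1 and 2 are both available.
- **Section 3.0** (schedule) collects the TSQM at early withdrawal, and Section 7.2 lists that visit among the analysed time points. Section 7.3 does not say whether its score is carried forward.
- **Sections 6.6 and 6.7** require PP patients to have completed Visit 4 (BID) or Visit 5 (TID).
- **Section 7.1** defines BID and TID by whether the patient titrated, which Section 3.0 bases on symptoms at Day 90.

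**The concern.** The primary objective is to measure satisfaction, so the estimated mean change is itself the result. The plan produces that estimate in two ways that treat leavers differently. LOCF holds a leaver at the last score used. Observed cases drop the leaver. Neither is named as the lead, and no assumption about why scores are missing is given against which either could be judged.

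If the two disagree, the plan cannot say which one answers the primary question. Section 1.0 treats the methods as open to justified change, and Section 9.1 leaves the switch to a non-parametric test open, so a named lead matters more. The repeated scores already scheduled would support a likelihood-based analysis that uses all of them.

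**Working it through.** **Inputs.** The SAP gives no effect size, SD, between-visit correlation, dropout rate or power, and its total of about 100 is not derived. There is no figure to reproduce, so every input below is assumed:

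- SD 20 and four visits (Days 0, 30, 60, 90), which is the BID endpoint
- dropout after Visit 2 of 10 to 30%
- log-odds of leaving rising by 0.03 to 0.08 per point of lower score
- three mean courses: rising (true change 15), flat after Visit 2 (10), early peak then fall (7)

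**Formulas.** Let Δ = Y4 − Y1, let p be the proportion leaving, and let L be a leaver's last recorded score.

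- LOCF bias = p × E[L − Y4 | leave]
- Observed-case bias = E[Δ | stay] − E[Δ] = p × (E[Δ | stay] − E[Δ | leave])

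LOCF is therefore unbiased only if leavers would on average have stayed at L. Observed cases are unbiased only if leavers and stayers have the same mean change. The second condition turns on the covariance between Δ and whatever drives leaving (variance 20² = 400):

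- Last score drives leaving, baseline correlation 0.3, on-treatment correlation 0.7: 400 × (0.7 − 0.3) = 160. Observed cases are biased upward.
- Last score drives leaving, exchangeable correlation 0.6: 400 × (0.6 − 0.6) = 0. No bias.
- Last score drives leaving, AR(1) 0.7: 400 × (0.49 − 0.70) = −84 at Visit 2 and 400 × (0.70 − 0.49) = +84 at Visit 3. These largely offset.
- Last change from baseline drives leaving, exchangeable 0.6: 400 × (0.6 − 0.6 − 0.6 + 1) = 160. The upward bias returns.

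**Simulated bias in points** (400,000 patients per row, 20% dropout, slope 0.08). The model is maximum likelihood with unstructured covariance and baseline in the response.

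| Leaving driven by | Correlation | Course | LOCF | Observed | Model |
|---|---|---|---|---|---|
| last recorded score | 0.3 / 0.7 | rising | −2.7 | +2.0 | 0.0 |
| last recorded score | 0.3 / 0.7 | flat | −1.4 | +2.0 | 0.0 |
| last recorded score | 0.3 / 0.7 | peak-fall | −0.1 | +2.0 | 0.0 |
| last recorded score | AR(1) 0.7 | flat | −1.7 | +0.1 | 0.0 |
| unseen current score | 0.3 / 0.7 | rising | −0.5 | +2.8 | +1.9 |
| unseen current score | 0.3 / 0.7 | flat | +0.8 | +2.8 | +1.9 |
| unseen current score | 0.3 / 0.7 | peak-fall | +2.0 | +2.8 | +1.9 |

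Reading the first row through the formulas: 2.7 / 0.20 = 13.5, so leavers' last scores lie 13.5 points below where they would have ended. Also 2.0 / 0.20 = 10, so stayers' mean change exceeds leavers' by 10 points.

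**Range.** For the rising course with 0.3 / 0.7 correlation and leaving by last recorded score, 10/20/30% dropout gives LOCF −1.4/−2.7/−3.9, observed cases +1.1/+2.0/+3.0 and model 0.0. With the weaker slope 0.03 and 20% dropout the figures are −2.0, +1.0 and 0.0. With slope 0.03 and the peak-fall course both planned methods err upward (+0.6 and +1.0).

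**Leaving by last recorded change from baseline** (SD 20, 20% dropout): LOCF −0.8 to −2.1, observed cases +1.5 to +3.0, model about 0.

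**Precision at n = 40** (rising, true 15.0, 20% dropout by last recorded score), mean (SD): LOCF 12.4 (3.8), observed 17.0 (4.2), model 15.0 (4.0). The two planned answers differ by 17.0 − 12.4 = 4.6 points.

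**Visit 2 requirement.** If some patients leave before Visit 2 (20% dropout in total) and the model keeps the Section 7.3 restriction, its bias is about −1.3. With all patients included it is 0.0.

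**Grouping by titration.** Suppose about 25% titrate on poor Day 90 status (rising course). The true change in the resulting BID group is 17.15, against 15.04 in all patients. Within the BID group the errors are LOCF 13.91 − 17.15 = −3.24, observed 20.35 − 17.15 = +3.20, model 18.15 − 17.15 = +1.00.

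**The case against.** The strongest objection is that dissatisfaction arising after the last recorded score is at least as natural a reason to leave as a poor recorded score. The model is then biased upward, sometimes more than LOCF: +1.9 against −0.5 in the rising row. This stands. A reader might infer that a mixed model would avoid the errors of both planned methods; that is true only under missing at random.

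A reader might also infer that observed cases are invalid whenever leaving depends on earlier scores, or that the two methods always err in opposite directions. Neither follows. Observed cases were within 0.1 point of the truth when leaving followed the last score under AR(1) or exchangeable correlation, and the signs can agree.

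Nor are there four competing answers (LOCF or not, ITT or PP). PP requires completion, so LOCF changes little there, and ITT without LOCF at the final visit is close to a completer analysis too. The real divide is ITT with LOCF against the rest. Section 7.3 can be read as making LOCF the default, but Section 9.1 gives the two approaches equal standing.

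The early-withdrawal score could make LOCF less stale than simulated. The SAP does not say whether it is used, and that gap needs closing under any method.

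The simulated dropout does not describe TID patients, who all passed Day 90 before the change of dose. For them, LOCF to Visit 5 can carry forward a score given before that change.

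Finally, the biases are mostly smaller than one standard error at n = 40, and no confirmatory decision depends on them. This limits the weight of the point.

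**Conclusion.** The point holds in a conditional form. Section 9.1 offers only LOCF and observed-case paired tests, with no lead and no missing-data assumption. When dropout depends on recorded scores, LOCF is generally biased and observed cases can be biased the other way. Under the assumed inputs each error is roughly 1 to 4 points at 10 to 30% dropout, though smaller for some courses and correlations. In that setting a likelihood-based repeated-measures model fitted to all patients is unbiased, with similar precision (SD 4.0 against 4.2 and 3.8 at n = 40). When unseen dissatisfaction drives leaving, the model is biased too: +0.4 to +3.0 points across the scenarios run.

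The model also does not undo the selection made by defining BID and TID from Day 90 titration.

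Only direction and order of size should be relied on, because SD, correlation, course and dropout are all assumed. What is at risk is a misestimated and ambiguous mean change in an open-label, single-arm study with exploratory p-values. The change is worth making, but the plan is not unusable without it.

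**What to change.** In Section 9.1, and for the matching change analyses in 9.2:

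1. Make one mixed model for repeated measures in ITT the lead analysis. Put all visits including baseline in the response, treat visit as categorical, and use an unstructured covariance with a named simpler fallback for the small TID group.
2. Report the end-of-treatment minus baseline contrast with its 95% CI.
3. Include every patient with any score; do not apply the Visit 2 requirement of Section 7.3 to this model.
4. State the missing-at-random assumption, and state how the early-withdrawal TSQM score enters (assigned to a visit, used only in a sensitivity analysis, or not used).
5. Keep observed-case, LOCF and PP as sensitivity analyses, and add a delta-adjusted missing-not-at-random analysis.
6. Say in the text that the BID and TID estimates describe groups formed by Day 90 titration, which the model does not correct.

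The cost is SAP wording, some added tables and a standard procedure in the software already planned; no new data are needed. The downsides are a missing-at-random assumption, a covariance assumption that may have to be simplified for TID, and the selection by titration, which remains.
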